## **7. STATISTICAL PLAN**

## 7.1 Sample Size Determination

The choice of sample size is based upon a comparison for the primary outcome (secondary procedures) of THA versus HA. All statistical hypotheses will be two-sided. Alpha levels of 0.05 for the primary and 0.01 for the secondary outcomes were chosen. Previous studies have reported secondary procedure rates in hip fracture patients treated with HA that have ranged from 4 to 10% at one year, with a weighted pooled risk of 5.3% (95% CI 3.2 to 8.9%) in a fixed effect meta-analysis, or 4.9% (95% CI 2.6 to 9.2%) using random effects. A pooled estimate from 5 randomized trials comparing THA with HA gave a relative risk of 1.67 (95% CI 0.86 to 3.24,  $p=0.13$ ) (**Table 3a**).

The sample size calculation reflects the proposed approach to the primary analysis, which will use the Cox proportional hazards model. The calculation is based on methods described by Collett (Collett, 1994). The goal is to calculate the required number of patients that will yield a sufficient number of outcome events (secondary procedures) in order to have adequate statistical power for a given size of treatment effect. This was done taking into account the anticipated secondary procedure rates in the HA group, postulated values of the relative risk increase associated with THA vs. HA, and the rates of mortality and loss to follow-up. Because some of these inputs are expected to change over the two year period of follow-up, the expected number of person-years of follow-up and the expected numbers of study events in each group were calculated, initially for the first year of follow-up; the calculation was then repeated for the second year of follow-up, after having estimated the number of patients in each group who would survive, be event-free, and available for continued follow-up between 12 and 24 months post-randomization.

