Based upon aggregate data from the pilot study, annual mortality rates of 15% and a loss to follow-up of 5% in each group were assumed, these rates applying to each of the two years of follow-up. Informed by the meta-analysis, the following assumptions were made: a one year risk of having a secondary procedure of 5% in the HA group and a risk of 1% in the second year. Various values of the relative risk reduction (HA vs. THA) were then used to identify the specific value that would correspond to a cumulative risk difference between THA and HA of 5% after 2 years. This figure was identified in a survey of participating surgeons as the minimally important difference to clinicians. Annual event risks by group were converted into equivalent hazard rates, assuming for simplicity that the hazard rate would be approximately constant within each of the two years. It is estimated that approximately 72% of the group receiving THA and 76% of the group receiving HA will be event-free and available for further follow-up at the start of the second year. The sample size was increased to allow for a combined 7.6% crossover rate from the assigned to the alternate treatment, based on pilot data. These assumptions lead to a required total sample size of 1,316 patients, which will yield an expected number of 96 secondary procedures. The associated relative risk reduction (RRR) is 0.45.

These calculations were repeated after replacing the 5% event risk at one year for HA by 4% and 6% and leaving the other factors unchanged (**Table 3b**). To account for potential surgeon level effects, the sample size has been further increased by 9% to 1,434.

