## 7.2 Statistical Methods

### 7.2.1 Primary Analyses

All outcome analyses will be performed by an intention to treat approach. To evaluate the effect of total hip arthroplasty versus hemi-arthroplasty on time to secondary procedures (the primary outcome), a Cox proportional hazards model will be used with the following covariates:

1. Age (i.e., 50-80 years or >80 years).
2. Pre-fracture living setting (i.e., institutionalized or not institutionalized).
3. Pre-fracture functional status (i.e., using aid or independent ambulator).
4. American Society for Anesthesiologists (ASA) Class (i.e., Class I/II or III/IV/V).
5. Centre number.

Results will be reported as hazard ratios with 95% confidence intervals. Kaplan-Meier curves will be constructed.

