### 7.2.4 Frequency of Analysis

The approach to interim analyses is guided by a desire to avoid spuriously inflated estimates of treatment effect (Montori et al, 2005; Briel et al, 2009). A single interim analysis will be performed when 60% of the planned patient-years of follow-up have been accrued. The data analyst will present the results of these analyses to our independent Data Monitoring Committee (see Section 8.4). The committee will be guided by the O'Brien-Fleming stopping rule based on the primary outcome, which will maintain the overall specified type I error rate at 5% for the combined interim and final analyses. According to this rule, the required p-value to declare a significant result at the interim analysis is 0.00762, and at the final analysis, the required p-value is 0.0476. The rule is conservative, making it difficult to stop the trial early unless a large treatment effect is observed. We will only apply our stopping rule to the primary outcome. The secondary functional outcomes may demonstrate significance quickly due to the nature of the instruments, but we will not stop the study for that reason. No one other than committee members will be aware of the data on which the committee makes its decision, and no one involved in the study will be aware of the content of their deliberations.

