2.8 Statistical Analyses for Primary and Secondary Outcomes

Analyses included patients in the groups to which they were assigned. Patients were censored at 24 months of follow-up or at the time of their last follow-up for patients lost to follow-up. The primary analysis was a proportional hazards model using a competing risk analysis (death as the competing risk) with time to the HEALTH primary study endpoint as the outcome. The independent variable was THA versus HA, and the following covariates were used: age (50-80 years or >80 years), pre-fracture living setting (institutionalized or not institutionalized), pre-fracture functional status (using aid or independent ambulator), and ASA Class (Class I/II or III/IV/V). For these covariates, we used values that were entered into the minimization system at time of enrollment. For our competing risk analyses, we used the method described by Zhou et al. to account for clustering within surgeons.⁶ The estimates from the competing risk analysis for clustered data analyses were marginal estimates. We report the treatment effects as hazard ratios (HRs) with 95% confidence intervals (CIs). No adjustment for multiplicity was made and the 95% CIs do not adjust for multiplicity. Kaplan-Meier curves were constructed for the primary outcome.

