Cox proportional hazards modeling was used to estimate the relative effect of THA versus HA on time to mortality, serious adverse events, and hip-related complications, separately, and included the same independent variables as listed for the primary analysis as well as including surgeon as a random effect. The hip-related complications analysis was a competing risk analysis with death as the competing risk. The estimates from the competing risk analysis for clustered data analyses were marginal estimates. We report the HRs and 99% CIs for the proportional hazards models. We performed proportional hazards regressions only for hip-related complications in which there were at least 50 events. Using multi-level models, the effect of THA versus HA on quality of life (SF-12, EQ-5D), function (WOMAC), and mobility (TUG) were estimated separately. Randomized treatment, visit (entered as a categorical variable) were also included as independent variables. Because we believed that the effect of THA versus HA may change over time, we also included an interaction term between treatment and visit. When the interaction term between treatment and visit was not statistically significant at $\alpha=0.05$, we removed it from the model. When the interaction term was significant, we reported the treatment effect at each visit. We accounted for death via joint modelling, using the method described by Rizopoulos.⁷ The SF-12, WOMAC, and EQ-5D were summarized using mean difference (MD) and 99% CIs. We analyzed the TUG as a dichotomous outcome with the following categories: a) patients who complete the test in ≤ 12 seconds, and b) those who require >12 seconds to complete the test or were unable to complete the test. We selected 12 seconds as the cut-off because this was the threshold used by the Centers for Disease Control and Prevention.⁸ The TUG was summarized using odds ratios and 99% CIs. For our multi-level analyses of quality of life, function, and mobility, all available data were used with no imputation performed. The models do not require that a patient have valid scores at all follow-up visits. We chose alpha levels of 0.05 and 0.01 for the primary and secondary outcomes, respectively. When scoring the WOMAC domains, we used the mean of the items that were answered in our calculation if at least 4 of the 5 pain items were answered, at least 1 of the 2 stiffness items were answered, and if at least 14 of the 17 function items were answered. If there were less items answered, the domain was set to missing. To calculate the WOMAC total score, we required non-missing scores for all 3 domains.

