2.11 Interpretation of Blinded Data

Hypothesis: We hypothesize that THA will have similar or lower rates of secondary procedures and higher functional outcome scores at 24 months compared with HA.

Here, we present alternative interpretations of blinded preliminary results. Blinded data interpretation may decrease the frequency of misleading data interpretation. Widespread adoption of blinded data interpretation with a minimum set of recommendations should be widely adopted.¹⁰

Secondary procedures over two years did not differ between treatment groups X and Y. The Kaplan Meier curve for the primary outcome suggests that the hazard ratios (HRs) remain constant up to 1 year (HR=1.30, 95% CI 0.86-1.95, $p=0.217$; non-significant estimates favoring treatment Y) and suggested estimates favouring treatment X after 1 year (up to 2 years) (HR=0.24, 95% CI 0.08-0.73; $p=0.011$).

Deaths did not differ between treatment groups X and Y over a 2-year period ($p=0.493$).

Serious adverse events ($p=0.052$) and hip-related complications ($p=0.277$) between treatment groups X and Y did not differ over a 2-year period.

Treatment X demonstrated significantly better overall WOMAC and EQ-5D utility scores ($p<0.05$) compared to Treatment Y (and trended towards better SF-12 PCS scores) over a 2-year period. TUG scores (cut-off 12 seconds) did not differ between treatment groups ($p=0.181$).

Subgroup analyses did not show any differences in the treatment effect between different subgroups ($p>0.05$).

Given the above preliminary findings, the more plausible hypothesis follows. Treatment X is THA and Treatment Y is HA. THA does not result in a statistically significant difference in secondary procedure rates over a 2-year period compared to HA; however, our findings suggest THA may have more secondary procedures earlier (less than 1 year, possibly driven by higher dislocations *results still blinded*) and HA may have more secondary procedures after 1-year post-fracture in those who did not have a secondary procedure during the first year. Functional outcome scores over 2 years favour THA compared to HA. These differences in function are small (although statistically significant). A lack of difference in secondary procedures, hip-related complications, and deaths, a lack of subgroup effects, and modest improvements in function render THA mildly superior to HA over 2 years. It's not unreasonable to consider the two treatments similar given

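### Does the SAP's alpha of 0.05 for the primary outcome drop the protocol's final-analysis level of 0.0476?

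*SAP*

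**What the plan says.** Protocol 7.1 sets the levels: "Alpha levels of 0.05 for the primary and 0.01 for the secondary outcomes were chosen". All hypotheses are two-sided.

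Protocol 7.2.4 then divides the primary 0.05 between two looks. One interim analysis takes place at 60% of planned patient-years under an O'Brien-Fleming rule on the primary outcome, "which will maintain the overall specified type I error rate at 5% for the combined interim and final analyses". The interim threshold is 0.00762, and "at the final analysis, the required p-value is 0.0476".

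Protocol 7.2.1 fixes the reporting format for the primary outcome: "Results will be reported as hazard ratios with 95% confidence intervals".

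SAP 2.8 states "We chose alpha levels of 0.05 and 0.01 for the primary and secondary outcomes, respectively". It also reports a 95% interval for the primary hazard ratio and says that neither the analysis nor those intervals are adjusted for multiplicity. It does not mention the interim analysis, 0.00762 or 0.0476, and nor does the rest of the available SAP. The part of the SAP before its section 2.0 was not available for this review.

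**The concern.** SAP 2.8 is the section on the primary and secondary analyses, and its only threshold for the primary outcome is 0.05. It does not call this the overall level, and it does not say whether the interim test was done, although it is written in the past tense and could have said so. A reader with only that section could test the final result at 0.05 after an interim look at 0.00762. Total error would then exceed 5%, and a final p-value of, say, 0.049 would count as significant when protocol 7.2.4 says it is not. The statement that nothing was adjusted for multiplicity could reinforce that reading.

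**Working it through.** **Inputs.** From protocol 7.2.4: one look at information fraction t = 0.60, interim p = 0.00762, final p = 0.0476, overall 5% two-sided. From protocol 7.1: 96 expected events, relative risk reduction 0.45.

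**1. The protocol's thresholds.** The O'Brien-Fleming-type spending function at one-sided 0.025, doubled, gives

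p₁ = 4 × [1 − Φ(2.2414/√0.60)] = 4 × [1 − Φ(2.8936)] = 4 × 0.001904 = 0.00762.

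The interim and final statistics are bivariate normal with correlation √0.60. Solving for the final level that makes the total crossing probability 0.05 gives 0.0476. Both figures reproduce, so 0.05 in protocol 7.1 is the total and 0.0476 is the share left for the final test. The two numbers are consistent.

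**2. If 0.05 were used at the end.** The same calculation with interim p = 0.00762 gives:

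| Final level | Overall two-sided error, t = 0.60 |
|---|---|
| 0.0476 | 5.00% |
| 0.05 | 5.23% |

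Under no effect, the two rules disagree with probability 5.23% − 5.00% = 0.23 percentage points. If no interim test was done, a single test at 0.05 has exactly 5% error and the question disappears.

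**3. Information fraction.** The look is timed by patient-years, not events. Protocol 7.1 assumes a risk in the hemi-arthroplasty group of 5% in year 1 and 1% in year 2, so events come earlier than patient-years, and 60% of patient-years should hold more than 60% of events. With those risks, 15% annual mortality, 5% annual loss and uniform accrual over 2 to 8 years (an assumption, since the documents give no accrual period), the event fraction is about 75% down to 64%. Overall error with a final 0.05 is then:

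| Event fraction | Overall error, final 0.05 |
|---|---|
| 64% | 5.20% |
| 65% | 5.19% |
| 70% | 5.14% |
| 75% | 5.10% |

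A fraction below 60% would need something else, such as a look restricted to events already adjudicated. At 50% the error would be 5.32%.

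**4. Distance between the two thresholds.** With 96 events and 1:1 allocation, SE(log HR) ≈ 2/√96 = 0.204. The smallest significant hazard ratio is exp(1.960 × 0.204) = 1.492 at 0.05 and exp(1.981 × 0.204) = 1.498 at 0.0476. For a hazard ratio of 0.55, |log HR|/SE = 0.598/0.204 = 2.929. Power is Φ(2.929 − 1.960) = 83.4% at 0.05 and Φ(2.929 − 1.981) = 82.8% at 0.0476, before any crossover allowance.

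**5. Interval.** A final level of 0.0476 corresponds to a 95.24% interval. It is wider on the log scale by 1.981/1.960 = 1.011, or 1.1%. The 95% interval in SAP 2.8 is what protocol 7.2.1 prescribes, and the SAP already says it is unadjusted.

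**The case for a change.** The strongest case for a change is that a threshold should be explicit in the section that defines the analysis, and should not rely on the result falling far from the boundary. Protocol 7.1 is read together with 7.2.4, and SAP 2.8 carries over only the first of the pair. SAP 2.9 and 2.10 say openly where they go beyond the protocol. SAP 2.8 does not always do so: it moves to a competing-risk model and leaves centre out of the covariates without comment. Its silence on 0.0476 therefore cannot prove that nothing changed. The remedy would cost a sentence or two and no data.

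Part of this stands. The available SAP does not say whether the interim test was done, and a cross-reference to protocol 7.2.4 would help the reader. But the alpha sentence has the same content as the protocol's own, and in the protocol that content is compatible with 0.0476. Where the SAP changes the model, it states a different model. Here it states the same level. The interim may also be described in the part of the SAP that was not available, so its absence from the plan as a whole has not been shown.

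**Conclusion.** This is a gap that analysts fill sensibly, and no change to the plan follows. SAP 2.8 restates the overall 5%, and protocol 7.2.4, which is still in force, says how that 5% is divided. If the interim took place, the final test is at 0.0476. If it did not, 0.05 is correct. A revision would only repeat this rule or record what was done.

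If someone did use 0.05 after an interim at 0.00762, the overall error would be 5.23% at 60% information, and about 5.10% to 5.20% at the event fractions of 64% to 75% that the protocol's front-loaded risk suggests. These figures rest on the bivariate normal approximation and, for the event fractions, on the assumed accrual period. Only a final p-value between 0.0476 and 0.05 would be judged differently. SAP 2.11 gives no overall p-value for the primary outcome, but it summarises the blinded result as "Secondary procedures over two years did not differ between treatment groups X and Y", so a changed conclusion is unlikely.

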2.9 Subgroup Analyses and Hypothesized Effects

At the trial onset, we specified in the trial protocol that no subgroup analyses would be conducted. However, towards the end of the trial, prior to unblinding, the following subgroup analyses were decided upon and were conducted to investigate the following prognostic factors as possible effect modifiers. The HEALTH primary endpoint was the dependent variable for these analyses. For these subgroup analyses, we used the data from our database. What was captured in the database reflects the true values for these factors, which may be different than what was originally entered into the minimization system at time of enrollment.

1. Age (i.e., 50-80 years or >80 years): Hypothesized that THA will be better relative to HA in the younger subgroup than in the older patients.
2. Pre-fracture living setting (i.e., institutionalized or not institutionalized): Hypothesized that THA will be better relative to HA in those not institutionalized than those institutionalized.
3. Pre-fracture functional status (i.e., using aid or independent ambulator): Hypothesized that THA will be better relative to HA in independent ambulators than in those using an aid.
4. American Society for Anesthesiologists (ASA) Class (i.e., Class I/II or III/IV/V): Hypothesized that THA will be better relative to HA in Class I/II than in Class III/IV/V.

These subgroup analyses were performed (separately) by including the subgroup factor as an independent variable in our proportional hazards regression model along with an interaction term between it and randomized treatment. We used the criteria suggested by Kasenda et al. to guide inferences about the credibility of our subgroup analyses.⁹

After unblinding, we identified three post hoc subgroup analyses and performed them as follows:

1. Added a three-category age (50 to 70 years or 71 to 80 year or ≥ 81 years) as an independent variable in our proportional hazards regression model along with an interaction term between it and randomized treatment. We hypothesized that THA will be better relative to HA in the youngest subgroup than in the older patient subgroups.
2. Added a three-category age (50 to 70 years or 71 to 80 year or ≥ 81 years) as an independent variable and interaction of age with treatment group into our final WOMAC total score model. We hypothesized that THA will be better relative to HA in the youngest subgroup than in the older patient subgroups.
3. Added country (Canada or Netherlands or USA or Australia or Norway or Spain or UK or Finland or New Zealand or South Africa) as an independent variable in our proportional hazards regression model along with an interaction term between it and randomized treatment. We hypothesized no difference across countries in treatment effects.

2.10 Sensitivity Analyses

At the trial onset, we did not specify in the trial protocol that any sensitivity analyses would be conducted. However, towards the end of the trial, prior to unblinding, we decided to conduct the following sensitivity analyses, with the HEALTH primary endpoint as the dependent variable:

- a) The primary analysis without including surgeon as a random effect
- b) The primary analysis with country included as an independent variable
- c) A per-protocol analysis
- d) An as-treated analysis
- e) Unstratified proportions analyses where we made varying assumptions about risk of event in those who were lost to follow-up

2.11 Interpretation of Blinded Data

Hypothesis: We hypothesize that THA will have similar or lower rates of secondary procedures and higher functional outcome scores at 24 months compared with HA.

Here, we present alternative interpretations of blinded preliminary results. Blinded data interpretation may decrease the frequency of misleading data interpretation. Widespread adoption of blinded data interpretation with a minimum set of recommendations should be widely adopted.¹⁰

Secondary procedures over two years did not differ between treatment groups X and Y. The Kaplan Meier curve for the primary outcome suggests that the hazard ratios (HRs) remain constant up to 1 year (HR=1.30, 95% CI 0.86-1.95, $p=0.217$; non-significant estimates favoring treatment Y) and suggested estimates favouring treatment X after 1 year (up to 2 years) (HR=0.24, 95% CI 0.08-0.73; $p=0.011$).

Deaths did not differ between treatment groups X and Y over a 2-year period ($p=0.493$).

Serious adverse events ($p=0.052$) and hip-related complications ($p=0.277$) between treatment groups X and Y did not differ over a 2-year period.

Treatment X demonstrated significantly better overall WOMAC and EQ-5D utility scores ($p<0.05$) compared to Treatment Y (and trended towards better SF-12 PCS scores) over a 2-year period. TUG scores (cut-off 12 seconds) did not differ between treatment groups ($p=0.181$).

Subgroup analyses did not show any differences in the treatment effect between different subgroups ($p>0.05$).

Given the above preliminary findings, the more plausible hypothesis follows. Treatment X is THA and Treatment Y is HA. THA does not result in a statistically significant difference in secondary procedure rates over a 2-year period compared to HA; however, our findings suggest THA may have more secondary procedures earlier (less than 1 year, possibly driven by higher dislocations *results still blinded*) and HA may have more secondary procedures after 1-year post-fracture in those who did not have a secondary procedure during the first year. Functional outcome scores over 2 years favour THA compared to HA. These differences in function are small (although statistically significant). A lack of difference in secondary procedures, hip-related complications, and deaths, a lack of subgroup effects, and modest improvements in function render THA mildly superior to HA over 2 years. It's not unreasonable to consider the two treatments similar given

small differences in functional scores. The extra cost of THA to the modest benefits in function may not render it the primary implant of choice in this patient population.

If treatment X is HA and treatment Y is THA, then HA does not result in a statistically significant difference in secondary procedure rates over a 2-year period compared to THA. However, our findings suggest HA may have more secondary procedures earlier (less than 1 year) and THA may have more secondary procedures after 1-year post-fracture, in those who did not have a secondary procedure during the first year. Further, functional outcome scores over 2 years favour HA compared to THA. These differences in function are small (although statistically significant), and somewhat unexpected. A lack of difference in secondary procedures, hip-related complications, and deaths, a lack of subgroup effects, and modest improvements in function render HA mildly superior to THA over 2 years. It's not unreasonable to consider the two treatments similar given small differences in functional scores. However, the extra cost and added complexity of THA may not render it the primary implant of choice in this patient population.

REFERENCES

1. American Society of Anesthesiologists . ASA Physical Status Classification System. <https://www.asahq.org/resources/clinical-information/asa-physicalstatus-classification-system>. Published 2017. Accessed February 6, 2017.
4. Rabin R, de Charro F. EQ-5D: a measure of health status from the EuroQol Group. *Ann Med*. 2001;33(5):337-343.
7. Rizopoulos D. JM: An R Package for the Joint Modelling of Longitudinal and Time-to-Event Data. *J Stat Softw*. 2010;35(9):1-33.

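### SAP 2.11 splits the primary outcome at 1 year on the evidence of the Kaplan-Meier curve, and bases early and late implant statements on unplanned, unadjusted period hazard ratios, the early one non-significant

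*SAP*

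**What the plan says.** SAP 2.8 defines the primary analysis: "The primary analysis was a proportional hazards model using a competing risk analysis (death as the competing risk"), with follow-up censored at 24 months and one treatment term. Protocol 7.2.1 likewise has one Cox treatment effect. Neither includes a treatment-by-time term or separate periods for the primary outcome. The subgroup analyses in SAP 2.9 and the sensitivity analyses a) to e) in SAP 2.10 do not split follow-up time. SAP 2.8 says that multiplicity is not adjusted for.

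SAP 2.11 opens its results with "Secondary procedures over two years did not differ between treatment groups X and Y". It then says: "The Kaplan Meier curve for the primary outcome suggests that the hazard ratios (HRs) remain constant up to 1 year". The early estimate is printed as "HR=1.30, 95% CI 0.86-1.95, $p=0.217$; non-significant estimates favoring treatment Y". The estimate from 1 to 2 years is 0.24 (95% CI 0.08 to 0.73, p=0.011), favouring X.

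Both label scenarios use the split. If X is THA: "our findings suggest THA may have more secondary procedures earlier (less than 1 year, possibly driven by higher dislocations", and "HA may have more secondary procedures after 1-year post-fracture in those who did not have a secondary procedure during the first year". If X is HA: "our findings suggest HA may have more secondary procedures earlier (less than 1 year) and THA may have more secondary procedures after 1-year post-fracture".

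**The concern.** The period hazard ratios are extra looks at the primary endpoint, and the text attributes the split to the shape of the observed curve. A p-value from a window chosen that way does not have its nominal error rate. Blinding to the arm labels does not repair this, because the curves separate or cross in the same way whatever the arms are called.

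The two halves of the message have different weaknesses. The early half is a difference whose interval includes 1. The results text says so, but the conclusions do not repeat it. The late half compares only patients who reached 1 year without an event. Protocol 7.1 expected about 72% of the THA group and 76% of the HA group to be event-free and available at that point, so the late comparison is not one between the groups as randomized.

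The question actually being asked is whether the treatment effect changes over time, and no test of that is reported. SAP 2.8 handles this question differently for the functional outcomes: it tests the treatment-by-visit interaction first, and reports effects by visit only if that test is significant. At stake is a directional early/late message about the implants, sitting beside a null primary result.

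**Working it through.** **Inputs.** From SAP 2.11: early HR 1.30 (0.86 to 1.95), p=0.217; late HR 0.24 (0.08 to 0.73), p=0.011. From SAP 2.8: alpha 0.05 for the primary outcome and 0.01 for secondary outcomes. From protocol 7.1: two-sided tests, 96 expected events, and HA risks of 5% in year 1 and 1% in year 2, so about 5/6 = 83% of events fall in year 1.

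**1. Reproduce the printed p-values.** SE = (ln upper − ln lower)/3.92 and z = ln(HR)/SE.
- Early: SE = ln(1.95/0.86)/3.92 = 0.209; z = 0.262/0.209 = 1.26; p = 0.209. Rounding of the printed figures allows 0.198 to 0.220, which contains 0.217.
- Late: SE = ln(0.73/0.08)/3.92 = 0.564; z = −1.427/0.564 = −2.53; p = 0.0114. Rounding allows 0.008 to 0.016, which contains 0.011.

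Both printed results are internally consistent. Their inverse-variance average is HR 1.06 (0.72 to 1.56), in keeping with the null 24-month statement. SAP 2.11 does not print the overall hazard ratio.

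**2. Error rate of two period tests.** If independent, 1 − 0.95² = 0.0975. A null simulation with the cut fixed at 12 months gives about 10%. If the cut is picked after seeing the data, the rate depends on how many cuts were in play, which the documents do not say. With five or six assumed candidate cuts, and 96 to 112 assumed events, simulations give about 23 to 26% for at least one period with p<0.05.

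**3. Events behind the late hazard ratio.** Take SE² ≈ 1/d₁ + 1/d₂, with events in a ratio near 0.24. For 4 and 16 events, √(1/4 + 1/16) = 0.559, close to 0.564. So the late result rests on roughly 20 events. This ignores clustering, covariates and unequal numbers at risk.

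**4. Robustness of the late result.** Bonferroni for two periods: 2 × 0.011 = 0.022. For four tests it is 0.044, and for five 0.055. The 99% interval, which is the level the SAP uses for secondary outcomes, is 0.056 to 1.03.

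**5. The test that fits the question.** Difference of log hazard ratios: 0.262 + 1.427 = 1.689. SE = √(0.209² + 0.564²) = 0.601. z = 2.81, nominal p = 0.005. Ratio of hazard ratios = 1.30/0.24 = 5.4 (95% CI 1.7 to 17.6), treating the two periods as independent. Allowing for a choice among five assumed cuts raises p to about 0.02.

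**The case against.** SAP 2.11 records how blinded results were read. It is not an analysis rule, and its value lies in having been fixed before the labels were known. Its statements are hedged, the early estimate is called non-significant where it is printed, and the restriction to patients without a first-year procedure is stated in both scenarios. The closing assessments rest on the lack of overall differences and on modest functional gains, not on the period hazard ratios. The 1-year point also has a precedent: protocol 7.1 assumes an approximately constant hazard within each of the two years. Finally, the late p-value survives Bonferroni for up to four tests, and the interaction suggests that a changing effect may be real.

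Most of this stands, and it rules out several stronger readings:
- A reader might infer that nothing settles which contrast decides. The documents do not support that: SAP 2.8 names one 24-month analysis, and both conclusions open with its null result.
- A reader might take an error rate near 25% as established. It depends on assumed candidate cuts, and no text says that several were tried.
- A reader might say that SAP 2.9 required a post hoc label here. It uses that label only for analyses identified after unblinding, whereas 2.11 is written as still blinded.

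The precedent does not settle the matter. Protocol 7.1 uses the 1-year break as a sample-size simplification, no analysis section adopts it, and 2.11 itself attributes the split to the curve. Nor do the conclusions repeat that the early estimate was non-significant.

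**Conclusion.** The point holds as a reporting weakness in SAP 2.11, not as a threat to the primary result. The split is unplanned in the available text, and the two period tests together carry about 9.75% familywise error with a fixed cut, and more by an unknown amount if the cut was chosen from the data. The early statement has no support at 0.05. The late statement depends on roughly 20 inferred events in a selected population and would miss the 0.01 level.

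It would also go too far to call the early/late pattern spurious. The interaction computed from the printed intervals is nominally p about 0.005. The data therefore suggest non-proportional hazards, but they do not establish a separate early difference. These figures assume independent period estimates and Wald intervals. SAP 2.11 does not say whether the period hazard ratios come from the clustered competing-risk model of SAP 2.8.

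**What to change.** Leave the blinded interpretation as recorded; deleting sentences from it would undo its purpose. Add a dated note to SAP 2.11 that:
1. says the 1-year split was unplanned, prompted by the Kaplan-Meier curve, and exploratory;
2. reports one treatment-by-period interaction test (0 to 12 versus 12 to 24 months) as the basis for any early/late statement, mirroring the SAP 2.8 approach to functional outcomes, and names the model used;
3. gives event counts by arm and period;
4. states for both conclusions that the early difference was not significant (1.30, 0.86 to 1.95);
5. confirms that the 24-month contrast alone decides the primary result.

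The cost is one extra model term, a small table and a few sentences. The early/late message becomes less definite.
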